9.4 Registration and randomisation

9.4.1 Registration

Eligible participants with suspected sepsis will be identified at triage. After initial NEWS2 and structured assessment in line with local standard practice, the eligibility criteria will be assessed and if no exclusion criteria apply, patients will be enrolled and randomised.

9.4.2 Randomisation

Individual patients with suspected sepsis will be randomised in a 1:1 ratio to either standard clinical management (control) or standard clinical management plus PCT guided assessment (intervention). We will use minimisation with NEWS2 score and site as stratification factors and add a random element to reduce the risk of subversion. This will be implemented in a secure 24-hour web-based randomisation programme controlled centrally by the Centre for Trials Research in Cardiff.

10 Trial Intervention

PRONTO uses both the BRAHMS PCT-direct and the PathFast BRAHMS PCT. Both readers are fully validated, CE-marked point-of-care tests to determine levels of Procalcitonin in the blood. Readers for the BRAHMS PCT-Direct and all required reagents for Quality Control tests will be provided by ThermoFisher as part of a supplier agreement. The test requires 20 µl blood which will be obtained from either venous blood during standard care procedures at

triage or via a finger-prick. Recruitment using BRAHMS PCT Direct will continue until end of May 2023

From December 2022 six high recruiting sites will transition from BRAHMS PCT Direct to use the PathFast BRAHMS PCT. Readers, cartridges and associated reagents for Quality Control tests will be provided by AB Scientific as part of a separate supplier agreement. This test requires 100 µl blood which may need to be obtained as a separate venepuncture in situations where standard care phlebotomy has been completed before the PCT test is requested. These six sites will continue to recruit until the end of the study.

This will be used in combination with NEWS2 assessment of adult patients with suspected sepsis in ED, using a guidance-only algorithm for clinicians (see flow chart). It is important to note that clinicians have oversight at all times as to whether to adhere to the algorithm. As currently mandated in NICE clinical guidelines and quality standard QS161, urgent senior review within an hour will take place where any health care provider identifies at least one risk factor indicating high risk of severe illness or death regardless of aetiology. In the intervention arm a NEWS2 score of 5 or 6, combined with a PCT score of <0.5 indicates a low risk of bacterial sepsis, but an urgent senior review is mandated on the basis of the elevated NEWS2 score in keeping with standard QS161. For participants who are identified as medium risk, urgent senior review will occur. Antibiotics will be delivered according to clinical assessment. For participants in the high risk categories (Figure 1, red boxes), antibiotics will be given within the hour along with blood tests and IV fluids given as per standard care.

The PCT result is a decision aid and not to be used as a definitive management decision tool. Trained HCPs will perform the test in the ED, without the need to send the PCT sample to the laboratory. A rapid result, especially if it indicates a low or medium risk, may provide reassurance to patients and families, and reduce anxiety.

[figure not shown]
Full administrator level training will be provided by Thermofisher or AB Scientific at each site with all users following the appropriate Standard Operating Procedure for QC measurement and routine work flow processes (see example of BRAHMS PCT Direct in Figure 3). For the BRAHMS PCT Direct, Research Nurses or appropriately delegated HCPs will have a unique 4-

digit log in code for the reader. Adults in the control arm will not have the PCT test performed and will simply have NEWS2 assessment for suspected sepsis as per standard care.

Thermo Scientific B·R·A·H·M·S direct Reader

Routine workflow

1/3

thermo scientific

Figure 3. Routine work flow for BRAHMS PCT-Direct Reader.

10.1 Adherence

Adherence to the algorithm will be recorded on the CRF and will capture instances where the treating clinician overrules the algorithm if they feel it is appropriate to do so. The ultimate responsibility for clinical care of the patient lies with the treating clinician therefore the cut – off boundaries for initiation times of antibiotics are not mandatory but are recommended guidance to aid clinical decision making. The aim of the trial is to assess whether the use of PCT can improve decision making about which patients receive antibiotics and in what time period. Deviations from the algorithm will not be recorded as protocol violations.

11 Trial procedures

All participants will be prospectively enrolled in the trial from the date of randomisation and will be assessed up to and including day 28 or until they are discharged from clinical care (for those enrolled in the last three months of the trial). Assessments include antibiotic initiation, antibiotic use, adverse events, ICU usage (details of admission to ICU), unscheduled readmissions (ICU re-admissions, re-admissions post discharge), mortality (death for any reason in the 28 days following randomisation), discharge before Day 28, and serious adverse drug reactions (ADRs) to the antibiotic. All clinical management decisions will be recorded at all time points.

At Day 28 and Day 90 there will be a follow-up via telephone or electronically (email/text) about the healthcare utilisation and quality of life of the participant. If unsuccessful a questionnaire booklet will be posted to the participant for them to complete and return with a pre-paid envelope.

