11.1 Assessments

Outcome data will be recorded daily by the research nurse for all recruited participants (up to and including Day 28, or until discharge). Patient reported outcome data (health-related quality of life and resource use questionnaires) will be recorded at day 28 and day 90 (with the exception of those recruited within the last 3 months of the study).

Research nurses will review observation and medication charts, and medical notes for all recruited participants to collect the data described in Table 1 below:

Table 1: Outcome data collection

Outcome	Data Source	Type of data	Frequency	By Whom
Antibiotic (Abx) initiation	Observation (Obs) charts/medical notes/drug charts	Time of initiation, Abx type, dose, duration	Admission/Daily	Research Nurse
Abx use (IV and Oral) in-patient	Obs charts/medical notes/drug charts	Abx type, dose, duration	Daily	Research Nurse
Abx use (IV and Oral) post discharge up to 28 days	Obs charts/medical notes/drug charts/patient report/GP record	Abx type, dose, duration	At 28 day	Research Nurse
Adverse events	Obs charts/medical notes	Date, type	Daily	Research Nurse
ICU usage	Medical notes	Date, details of admission to ICU	Daily	Research Nurse
COVID diagnosis	Medical notes	Date, clinical or laboratory confirmed	At 28 day	Research Nurse
Unscheduled readmissions	Medical notes	ICU re-admissions, re-admissions post discharge	Daily	Research Nurse
Mortality	Medical notes	Date, Description	If before Day 28	Research Nurse
Discharge	Medical notes	Date, Description	If before Day 28	Research Nurse
Serious Adverse Drug Reactions (ADRs)	Medical notes	ADR(s)	Daily	Research Nurse
Health utility	Patient reported	-	Day 28 and Day 90	EQ-5D/5L, Patient reported questionnaire, collected by

				telephone or by post
Health-related Quality of Life (EQ-5D/5L)	Patient reported	-	Day 28 and Day 90	Patient reported, collected by telephone, or by post
Resource use	Patient reported	Direct medical costs and resource use	Day 28 and Day 90	Patient reported, collected by telephone, or by post

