23.2 Data Protection

Confidentiality of study data will be ensured. Participants will always be identified using only their unique study identification number and any additional identifiers.

The CTR will act to preserve participant confidentiality and will not disclose or reproduce any information by which participants could be identified, except where specific consent is obtained. Data will be stored in a secure manner and will be registered in accordance with the General Data Protection Regulation 2016/679. The data custodian for this trial is the Chief Investigator at Liverpool University (sponsor).

Participants will always be identified using their unique study identification number and any additional identifiers. This includes collection of NHS number (or equivalent – e.g. CHI number in Scotland), name and postcode to register and trace participants with NHS Digital.

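### Protocol Section 11 ends assessment, including co-primary 28-day mortality, at discharge for patients enrolled in the last three months; this contradicts the unconditional day-28 endpoint, and no post-discharge source of vital status is named for any patient

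*Protocol*

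**What the plan says.** - **Section 11 (Trial procedures).** Participants are assessed up to day 28 or "until they are discharged from clinical care (for those enrolled in the last three months of the trial"). The next sentence lists those assessments and includes "mortality (death for any reason in the 28 days following randomisation"), with no exception for late enrolees.
- **Section 11.1, daily recording.** Research nurses record outcomes "for all recruited participants (up to and including Day 28, or until discharge"). This applies to every recruit, not only late ones.
- **Section 11.1, questionnaires.** Quality of life and resource use are to be reported by patients at both follow-up contacts, "with the exception of those recruited within the last 3 months of the study". The sentence does not settle whether the exception covers both contacts or day 90 alone.
- **Table 1, Mortality row.** "Mortality Medical notes Date, Description If before Day 28 Research Nurse". No other source is given.
- **Synopsis and Section 5.3.** Follow-up is 28 days for the primary endpoint, and 28-day mortality is a binary co-primary outcome. Neither carries an exception.
- **Table 3 (Section 17.1).** The last-three-months footnote is attached only to the 90-day rows (time until death, EQ-5D-5L).
- **Section 23.2.** NHS number, name and postcode are collected "to register and trace participants with NHS Digital". The text does not link this to 28-day mortality.

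**The concern.** A three-month exception makes sense for 90-day outcomes, because patients enrolled near the close cannot complete 90 days. It has no such rationale at day 28. As worded in Section 11, it cuts off collection of a co-primary safety outcome at discharge, so the death at home on day 15 of a late recruit who had been sent home would not be sought.

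No other stated process would pick that death up. Table 1 offers medical notes only. Section 15.2 takes deaths out of SAE reporting because routine data collection is meant to record them. The NHS tracing is not tied to this endpoint. Section 10 has six sites recruiting to the end of the study, and no 28-day gap after the last enrolment is spelled out.

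Mortality is tested for non-inferiority. Deaths wrongly counted as survivals make the arms look more alike, which is the unsafe direction for such a test.

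**Working it through.** **1. The plan's own figures.** Section 16.2 takes 15% mortality in both arms, a 2.5-point margin, one-sided 5% and 90% power.

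n per arm = (1.645 + 1.282)² × 2 × 0.15 × 0.85 / 0.025² = 3,495 (unrounded normal quantiles), or 6,990 in total, against 7,002 stated (0.2% apart). Dropout: 7,002 / 0.95 = 7,371, against 7,372. Group-sequential inflation: 7,676 / 7,372 = 1.041, matching the stated figure of just over 4%. The design figures reproduce and are not in dispute.

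**2. The text side by side.**

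| Place | Who | What is truncated |
|---|---|---|
| Synopsis, Section 5.3 | everyone | nothing at day 28 |
| Section 11, follow-up sentence | last three months | all listed assessments, mortality included, at discharge |
| Section 11, mortality definition | everyone | nothing; any death within 28 days |
| Section 11.1, daily recording | everyone | recording at discharge |
| Section 11.1, questionnaires | last three months | patient-reported data, at day 28 and 90 or at day 90 only |
| Table 3 footnote | last three months | 90-day outcomes only |

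The first and third rows cannot both hold with the second. Table 1 does name post-discharge sources elsewhere: the row for antibiotics after discharge adds patient report and GP record at day 28. The Mortality row has no equivalent.

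**3. Size of the late cohort, f (even accrual assumed).**
- 24 months of recruitment (Section 13.1): 3/24 = 12.5%, and 7,676 × 0.125 = 960 patients.
- Study months 7-31 (Section 27): 3/25 = 12%, or 921 patients.
- Synopsis trial period, December 2019 to April 2024, 53 months: 3/53 = 5.7%, or 3/47 = 6.4% after six months of set-up. Call it 6%, or 461 patients.

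**4. Effect if missed deaths are coded as survivals.** Let s be the share of 28-day deaths that occur after discharge. The protocol gives no value; 10-40% is assumed, equal in both arms, with none captured in the late cohort. With k = 1 − f × s:

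- deaths missed ≈ 7,676 × f × 0.15 × s
- apparent excess when the truth is 2.5 points = 2.5 × k
- SE = √[p₁(1−p₁)/n + p₂(1−p₂)/n], with p₁ = 0.15k, p₂ = 0.175k and n = 7,676 × 0.95 / 2 = 3,646
- one-sided type I error = Φ[(0.025 − 0.025k)/SE − 1.645]

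| f | s | Deaths missed | Apparent excess (points) | SE (points) | Type I error |
|---|---|---|---|---|---|
| 12.5% | 10% | 14 | 2.469 | 0.859 | 5.4% |
| 12.5% | 40% | 58 | 2.375 | 0.846 | 6.7% |
| 6% | 10% | 7 | 2.485 | 0.861 | 5.2% |
| 6% | 40% | 28 | 2.440 | 0.855 | 5.8% |

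This is a single-look approximation that ignores the interim adjustment, site effects and covariates.

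**5. Effect if late discharged patients are treated as missing.** Section 16.3 plans complete-case analysis, with multiple imputation only above 20% missing. A late cohort of 6-12.5% would not trigger it on its own. Complete-case analysis would then drop discharged survivors along with the missed deaths, so the direction of any bias in the difference cannot be determined.

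**The case against.** The strongest reply is that Section 11 is one loose parenthesis set against several consistent statements: the synopsis, Section 5.3, the mortality definition in the very next sentence, and Table 3. The same Section 11 list includes readmissions after discharge, which could not be assessed if assessment stopped there. Table 1 has nurses returning to the notes at day 28 for COVID diagnosis and post-discharge antibiotics, with no late-recruit exception. Section 21 ties the end of the trial to final data capture for the endpoints, which implies follow-up past the last enrolment. Tracing identifiers are collected, and operational detail may sit in documents not shown. All of this makes it likely that full 28-day mortality is intended. It does not remove the contradiction or supply a source.

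Three stronger readings are tempting and are not supported:

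- **That the co-primary becomes in-hospital mortality for late recruits.** The protocol never redefines the endpoint. That would be a consequence of following Section 11 literally.
- **That waiving the day-28 contact loses the mortality data.** That contact collects healthcare use and quality of life and is not the named mortality source. The exception may also cover day 90 only. The phrase "up to and including Day 28, or until discharge" governs daily recording for all recruits, so it is not evidence of a late-recruit rule.
- **That the treatment difference is biased by a large part of the margin.** With f = 12% and shares of 20% in control and 40% in the PCT arm, the bias would be 0.12 × 15 × 0.20 = 0.36 points, 14% of the margin. Nothing in the protocol supports such a split. Likewise, 0.12 × 15 × (0.10 to 0.40) = 0.18-0.72 points is a fall in the overall mortality level, not in the difference between arms.

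**Conclusion.** The contradiction is real and concerns a co-primary safety endpoint. Section 11 ends mortality assessment at discharge for the last three months of enrolment; the synopsis, Section 5.3, the Section 11 definition and Table 3 do not. Separately, no post-discharge source of day-28 vital status is stated for any participant.

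The likely numerical effect of the late-cohort wording is modest. A true excess at the margin would appear as about 2.47-2.38 points with a 12.5% cohort, with type I error of about 5.4-6.7% instead of 5%; a 6% cohort gives about 5.2-5.8%. These figures rest on assumptions outside the protocol: even accrual, 10-40% of 28-day deaths after discharge, equal shares between arms, no capture, and missed deaths coded as survivals. The effect is nil if vital status is in fact obtained at day 28 from notes or tracing. The case for correction rests on the conflict in the text, not on a demonstrated bias.

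**What to change.** 1. In Sections 11 and 11.1, confine the last-three-months exception to day-90 items and, if intended, patient-reported items, in line with the Table 3 footnote.
2. State that vital status at day 28 is obtained for every randomised patient, whether or not discharged, subject to any withdrawal of permission to use data.
3. Name the post-discharge source in the Mortality row of Table 1, for example the NHS tracing for which identifiers are already collected under Section 23.2.
4. State in Section 21 that final data capture falls at least 28 days after the last enrolment.

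The sample size is unchanged (7,002 / 7,372 / 7,676). The cost is protocol wording, minor tracing work, and at most a 28-day gap between last enrolment and data lock.

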11.1 Assessments

Outcome data will be recorded daily by the research nurse for all recruited participants (up to and including Day 28, or until discharge). Patient reported outcome data (health-related quality of life and resource use questionnaires) will be recorded at day 28 and day 90 (with the exception of those recruited within the last 3 months of the study).

Research nurses will review observation and medication charts, and medical notes for all recruited participants to collect the data described in Table 1 below:

Table 1: Outcome data collection

Outcome	Data Source	Type of data	Frequency	By Whom
Antibiotic (Abx) initiation	Observation (Obs) charts/medical notes/drug charts	Time of initiation, Abx type, dose, duration	Admission/Daily	Research Nurse
Abx use (IV and Oral) in-patient	Obs charts/medical notes/drug charts	Abx type, dose, duration	Daily	Research Nurse
Abx use (IV and Oral) post discharge up to 28 days	Obs charts/medical notes/drug charts/patient report/GP record	Abx type, dose, duration	At 28 day	Research Nurse
Adverse events	Obs charts/medical notes	Date, type	Daily	Research Nurse
ICU usage	Medical notes	Date, details of admission to ICU	Daily	Research Nurse
COVID diagnosis	Medical notes	Date, clinical or laboratory confirmed	At 28 day	Research Nurse
Unscheduled readmissions	Medical notes	ICU re-admissions, re-admissions post discharge	Daily	Research Nurse
Mortality	Medical notes	Date, Description	If before Day 28	Research Nurse
Discharge	Medical notes	Date, Description	If before Day 28	Research Nurse
Serious Adverse Drug Reactions (ADRs)	Medical notes	ADR(s)	Daily	Research Nurse
Health utility	Patient reported	-	Day 28 and Day 90	EQ-5D/5L, Patient reported questionnaire, collected by

				telephone or by post
Health-related Quality of Life (EQ-5D/5L)	Patient reported	-	Day 28 and Day 90	Patient reported, collected by telephone, or by post
Resource use	Patient reported	Direct medical costs and resource use	Day 28 and Day 90	Patient reported, collected by telephone, or by post

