5.4 Secondary outcomes measure(s)

Time until initiation of IV antibiotic therapy

Late IV antibiotic initiation – antibiotics commenced after 3 hours

Number of days on IV antibiotics (during admission and total over the first 28 days).

Number of days on any antibiotic (during admission and total over the first 28 days).

Number of days on broad spectrum antibiotics (IV and oral), defined by number of days on an Access group of antibiotics as defined by WHO [AWaRe Classification Database](#) (during admission and total over the first 28 days).

ICU admission – at any point during admission

Length of ICU stay

Length of hospital stay

Adverse antibiotic outcomes

Readmission to hospital within 90 days

Mortality within 90 days (and time until death)

Health utility (EQ-5D/5L) at 28 and 90 days

Health resource usage

Feasibility of implementing PCT testing alongside NEWS2 scoring in EDs

Acceptability of implementing PCT testing alongside NEWS2 scoring in EDs, to patients, carers and clinicians

Planned stratification of all outcomes by COVID-19 diagnosis

6 Trial design and setting

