12.2 Lost to follow up

Data will be obtained from observation and medical notes or drug charts and will be entered into the trial database. We will ask participants who have provided deferred consent to provide contact details for members of the research team to contact them while attempting to make follow-up interviews at days 28 and 90. To minimise loss to follow up, interviews will be via telephone or electronic with both utilised where possible.

Participants will be identified as lost to follow-up if it is not possible to contact them directly for 4 weeks post day 90/hospital discharge.

13 Internal pilot and recruitment rates

We propose an internal pilot, using quantitative and qualitative data, during the first 12 months of recruitment (study months 7-16) to ensure our ability:

- to include appropriate patients,
- to implement the research process in such a way we do not delay treatment time inappropriately,
- to ensure that the results of the test are being considered and used by the treating clinicians.

The internal pilot phase will assess the site and patient absolute recruitment and consent rate, proportion of patients undergoing PCT assessments and the ability to collect the primary outcome data. Qualitative interviews with two staff per site will be conducted in order to understand how the research process and the PCT guided algorithm have integrated into their ED setting. These will be used to understand the quantitative data and provide areas for improvement in processes to enhance the efficiency of the trial.

The progression criteria have been designed to allow for mitigating strategies to be discussed to allow for some adaptation to recruitment processes. We will discuss the results with our Trial Steering Committee, before reporting to the NIHR HTA Programme, for permission to proceed. In accordance with the HTA guidance on internal pilot studies, we will exclude the first two months of recruitment from our calculation of the recruitment rate as we anticipate a 'lag phase' during which the first few sites are still being registered and participating clinicians develop confidence and competence in identifying and recruiting patients. We will constantly be assessing the criteria during the internal phase. To progress from the internal pilot to the full trial, we would be looking to utilise the following criteria in Table 2:

Table 2: Internal Pilot Criteria

Criteria (at month 9 of recruitment)	Level	Action

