Antibiotic usage	No of days on IV antibiotics No of days on all antibiotics No of days on broad spectrum antibiotics	In hospital	Linear regression
Antibiotic adverse outcomes	Anticipated drug reactions include: diarrhoea, C. difficile , acute kidney injury, hearing loss etc.	In hospital	Logistic regression
ICU usage	People admitted to ICU No of days in ICU	In hospital	Logistic regression Linear regression
Readmission to hospital	People with one or more readmissions	After discharge	Logistic regression
Mortality	Time until death	90* days	Cox regression
Health utility	EQ-5D-5L	90* days	Linear regression of transformed outcome measure

* Except for patients recruited during the last 3 months of the study.
Full details of all analyses will be provided in the PRONTO SAP.

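### The assessment schedule collects deaths only to day 28, although mortality and time until death are to be analysed to day 90, and the NHS Digital tracing is not linked to mortality

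*Protocol*

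**What the plan says.** What the Protocol requires:

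- Section 5.4 lists as a secondary outcome "Mortality within 90 days (and time until death").
- Table 3 (section 17.1) gives "Time until death" as the mortality measure, over 90 days, by Cox regression. A footnote exempts patients recruited in the last 3 months.
- Section 5.3 makes 28-day mortality a binary co-primary outcome.

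What the Protocol schedules:

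- Section 11 describes the assessment as "mortality (death for any reason in the 28 days following randomisation").
- Table 1 (section 11.1) has one mortality row: medical notes, date and description, "If before Day 28", research nurse.
- Section 11.1 says of nurse recording: "Outcome data will be recorded daily by the research nurse for all recruited participants (up to and including Day 28, or until discharge").
- Section 11 describes the day-28 and day-90 contacts as being "about the healthcare utilisation and quality of life of the participant". Section 11.2 adds readmission, re-treatment, hospital-acquired infection and resource use. Neither lists death or vital status.
- Section 12.2 states: "Participants will be identified as lost to follow-up if it is not possible to contact them directly for 4 weeks post day 90/hospital discharge".
- Section 23.2 says that identifiers are collected, including "name and postcode to register and trace participants with NHS Digital".

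**The concern.** The outcome list and the analysis table need to know who died, and when, up to day 90. The data-collection sections stop asking at day 28. A site that follows section 11 and Table 1 exactly has no instruction to record a death on, say, day 50. The day-90 contact is addressed to the participant and covers topics that a participant who has died cannot report on.

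Two things are at stake. The first is the 90-day Cox analysis: deaths that never enter the database cannot be events, so the analysis would carry a 90-day label with few or no events after day 28. The second is the 28-day co-primary, which is tested for non-inferiority with a 2.5-point margin. Incomplete ascertainment matters there because deaths missed at the same rate in both arms and counted as survivors shrink a true difference towards zero.

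**Working it through.** **1. Requirement against collection**

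| Item | Needed (5.3, 5.4, Table 3) | Scheduled (11, 11.1, 11.2) |
|---|---|---|
| Death to day 28 | Yes, co-primary | Yes, from medical notes |
| Death from day 28 to day 90 | Yes, secondary outcome and Cox model | No row, no named source |
| Vital status at the day-90 contact | Implied by the above | Not among the listed items |
| Central tracing | One possible source | Section 23.2 only; no outcome or time point named |

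The mortality row is hard to read as shorthand for wider follow-up. Where Table 1 intends data from after discharge it says so: the row for antibiotics after discharge adds patient report and GP record as sources. The mortality row adds neither.

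**2. Loss to follow-up**

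Section 12.2 defines loss by failure of direct contact and makes no exception for death. A participant who dies on day 50, and whose death is not known to the team, cannot be contacted and so meets the definition. No step before the classification asks for vital status.

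**3. The 28-day outcome**

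Two smaller mismatches arise. The timing in Table 1 excludes day 28, while sections 11 and 11.1 include it. Medical notes are also the only listed source, so a death outside hospital after discharge is captured only if it reaches those notes.

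The direction of any bias can be illustrated. Assume that 10% or 20% of deaths in each arm are missed and counted as alive, with true rates of 17.5% and 15%:

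- 10% missed: 0.9 x 17.5 - 0.9 x 15 = 15.75 - 13.50 = 2.25 points
- 20% missed: 0.8 x 17.5 - 0.8 x 15 = 14.0 - 12.0 = 2.0 points

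A true difference equal to the margin would then look smaller than the margin. The 10-20% is an assumption. Nothing in the Protocol indicates how many deaths, if any, would be missed.

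**4. Scale for the 90-day outcome**

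Inputs: 28-day mortality of 15% and a maximum sample size of 7676, both from section 16.2. Mortality between day 28 and day 90 is not given, so a range x is assumed.

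Deaths outside the Table 1 window = 7676 x x. Their share of all 90-day deaths = x / (0.15 + x).

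| Assumed x | Deaths among 7676 | Share of 90-day deaths |
|---|---|---|
| 2% | 154 | 0.02/0.17 = 11.8% |
| 4% | 307 | 0.04/0.19 = 21.1% |
| 6% | 461 | 0.06/0.21 = 28.6% |
| 8% | 614 | 0.08/0.23 = 34.8% |

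The counts are ceilings for each x. With the planned 5% dropout the base is 7676 x 0.95 = 7292, and the Table 3 exception for the last 3 months lowers it further. The shares do not depend on the base.

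The planned sample size is unaffected. The standard formula for 15% in both arms, a 2.5-point margin, one-sided 5% and 90% power gives 3495 per arm, 6990 in total, against the stated 7002.

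**The case against.** The strongest reply is that a source exists. Section 23.2 collects NHS number, name and postcode to trace participants, and tracing can supply deaths. This stands in part. A reader might infer that 90-day mortality has no possible data source, and the Protocol does not support that. But section 23.2 is a data-protection paragraph. It does not say that tracing will be used for deaths, at what time, or for which outcome, and the assessment schedule does not mention it.

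A second reply concerns section 12.2. Its definition follows text about reaching participants for interviews at days 28 and 90, so it may describe only failed questionnaire contact. That is fair. A reader might infer that the Protocol orders deaths to be recorded as losses or censored as non-response. It does not: a death known from notes, family or tracing need not be handled that way, and censoring rules belong to the statistical analysis plan. What remains is that the definition, read literally, catches an unknown death.

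Third, nurse follow-up does extend past discharge. Table 1 collects post-discharge antibiotics, readmissions and COVID diagnosis, and there is a day-28 contact. Section 11 ties the discharge cut-off to those enrolled in the last three months. This lowers the risk of missing community deaths before day 28, though none of these items is a vital-status check.

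Fourth, the boundary wording sits in the frequency column and is repeated for discharge, so it more plausibly says when a form is triggered than redefines the endpoint. That stands. Calling the outcome a 27-day one would be too strong.

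Finally, leaving detail to the statistical analysis plan or Data Management Plan is no answer to the main point, because the Protocol itself sets the source and window for mortality and sets them inconsistently.

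**Conclusion.** The inconsistency holds. Section 5.4 and Table 3 require deaths to day 90. Section 11 and Table 1 collect them to day 28, the day-90 contact does not ask about death, and the tracing in section 23.2 is not tied to any mortality outcome. A trial run strictly to the stated schedule would leave deaths between day 28 and day 90 out of a planned analysis.

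The number affected cannot be derived from the documents. Roughly one eighth to one third of 90-day deaths (12-35%) would fall outside the window, given the assumed 2-8% mortality between day 28 and day 90 and the Protocol's 15% at day 28. This is the share outside the Table 1 window, not a forecast of deaths lost, because tracing may in practice recover them.

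Severity is moderate. The main effect is on a secondary outcome. A reader might infer that the 28-day co-primary is unsound; the documents do not support that. Its definition, sample size and decision rule are untouched. What remains there is a one-day wording mismatch and the possibility that notes alone miss some out-of-hospital deaths.

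**What to change.** - **Table 1, mortality row.** Give the sources as medical notes plus NHS Digital tracing. Record date of death, and vital status at day 28 (inclusive) and at day 90. Apply this identically in both arms to all participants whose data may be used, with day 90 subject to the Table 3 exception for the last 3 months.
- **Section 11.** Extend the description of the mortality assessment to day 90 so that it agrees with section 5.4 and Table 3.
- **Section 12.2.** Require a vital-status check before anyone is classed as lost to follow-up, and state that a death is an outcome and not a loss.
- **Section 23.2.** State that tracing serves the 28-day and 90-day mortality outcomes.

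The cost is Protocol and case report form wording, a data request, and a short lag before the mortality data are final. The identifiers are already to be collected, and no extra patient contact is needed.
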